6.6 Dose Modification

Modification of the dose (benralizumab or placebo) is not permitted.

6.7 Intervention After the End of the Study

After the end of the study, the participant should be given standard of care therapy according to local practice, at the discretion of the Investigator.

7 DISCONTINUATION OF STUDY INTERVENTION AND PARTICIPANT DISCONTINUATION/WITHDRAWAL

7.1 Discontinuation of Study Intervention

Participants who prematurely discontinue from IP will be asked to come in for all visits and complete the study assessments at the IPD/EOT visit.

Discontinuation from IP does NOT automatically lead to a complete withdrawal from the study. Participants discontinuing from IP are strongly encouraged to continue in the study up to the study completion (Visit 16, Week 60) as described in Section 7.1.1.

Participants will be discontinued from IP in the following situations:

- Participant decision. The participant is at any time free to discontinue treatment, without prejudice to further treatment. The participant should always be asked about the reason(s) and presence of any AEs.
- AE that, in the opinion of the Investigator, contraindicates further dosing.
- Severe non-compliance with the CSP.
- Risk to participant as judged by the Investigator or AstraZeneca.
- Pregnancy.
- IP unblinding.
- Development of any of the following study-specific criteria for discontinuation:
 - Anaphylactic reaction to IP administration, in the opinion of the Investigator, requiring administration of epinephrine.
 - Development of helminth parasitic infestation requiring hospitalization.

Refer to the SoA (Table 3) and Section 7.1.1 (IPD visit) for data to be collected at the time of IPD and follow-up and for any further evaluations that need to be completed.

The reason for premature discontinuation of IP should be documented in the source documentation and recorded in the eCRF.

7.1.1 Procedures for Early Discontinuation of Study Intervention and at End of Study

A participant who decides to discontinue IP should always be asked about the reason(s) and the presence of any AEs. The reason for discontinuing treatment and the date of last IP administration should be recorded in the eCRF. Participants permanently discontinuing IP administration should be given locally available standard of care therapy, at the discretion of the Investigator. Discontinuation of IP will be registered in the IxRS.

See the SoA (Table 3) for data to be collected at the IPD visit and for any further evaluations to be completed.

7.1.1.1 Early Discontinuation of Study Intervention

All participants who prematurely discontinue IP should return to the study site for the IPD visit 4 weeks (\pm 7 days) after the last dose of IP for procedures, or as soon as feasible if this interval is missed (eg, if decision on discontinuation was made later), as specified in Table 3.

At the IPD visit, the participant will be offered the following options for further follow-up:

- Participants are encouraged to return to all scheduled site visits and perform all procedures (including PRO completion and blood draws), but without IP administration, until the end of the study (Visit 16).
- If the participant is unwilling or unable to attend the scheduled site visits until the end of the double-blind treatment period, he/she will be offered a follow-up option that includes monthly telephone contact instead. During follow-up telephone contact, the Investigator will collect information about concomitant medications, information on AD symptoms, and AE/SAE(s) (Section 8.3).

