AD, Atopic dermatitis; ADA, Anti-drug antibodies; AE, Adverse Event; BSA, body surface area; CSP, Clinical Study Protocol; EASI, Eczema Area and Severity Index; ECG, Electrocardiogram; CCI ; EoT, End of treatment; FSH, Follicle-stimulating hormone; HIV, Human

If an at-home PRO is available according to the assessment schedule in Table 4 but has not been completed prior to the site visit, then site staff will direct the participant to complete the assessment at the site before any other study procedures are conducted.

Table 4 Schedule of PRO Assessments

Instruments	Schedule									
Daily PRO at home: Peak Pruritus NRS	Every evening ^a . First assessment at home the day of V1.									
Periodic PROs: CCI , EQ-5D-5L, SF-36v2	At site at V1 and V2. At home every 28±3 days after V2 until V6 is confirmed. At site at V6, V7, V12, and V16. Required at IPD visit. Optional at unscheduled visit.									
Periodic PROs: POEM, DLQI/CDLQI, HADS, PGI- S, Patient-reported experience (free text entry)	At site at V1, V2, V3, V4, V5, V6, V9, V12, V15, and V16. Required at IPD visit. Optional at unscheduled visit. CDLQI will be assessed in participants \leq 16 years of age at V1; DLQI will be assessed in all other patients > 16 years of age.									
PRO at site: CCI	At site at V6 and V15. Required at IPD visit.									
Evening is defined as 17:00 to 23:59.										
CCI										
CCI CDLQI, The Ch	nildren's Dermatology Life Quality Index; DLQI,									
Dermatology Life Quality Index; EQ-5D-5L, European	Quality of Life-5 Dimensions; HADS, Hospital Anxiety									
and Depression Scale; IPD, Investigational product discontinuation; NRS, Numerical Rating Scale; CCI										
; PGI-S, Patient Global Impression of Severity; POEM, Patient										
Oriented Eczema Measure; PRO, Patient-reported outcome; SF-36v2, Short Form 36-item Health Survey										
Version 2; CCI ; V, Visi	it.									

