6.5.3 Rescue Medication

If medically necessary (ie, to control intolerable AD symptoms), rescue treatment for AD may be provided to study participants at the discretion of the investigator.

If medically necessary for intolerable AD symptoms that occur during the treatment or followup periods, rescue therapy with otherwise prohibited concomitant medications or therapies may be prescribed to participants at the discretion of the investigator. Rescue therapy is not permitted until at least Visit 3 (Week 4). Rescue therapy should only be prescribed after assessment of the participant in the clinic, either at a scheduled or unscheduled visit. A justification for each participant who commences rescue therapy must be documented by the investigator in the clinical notes.

Rescue therapy should initially be restricted to topical therapies (ie, TCSs or TCIs, or any other topical anti-inflammatory treatment [eg, PDE4 inhibitor]). TCSs should be prescribed at the lowest potency appropriate for the situation. TCIs should be reserved for problem areas only (eg, face, neck, or intertriginous and genital areas). Systemic rescue therapy should be reserved for participants who do not adequately respond to topical rescue therapy after ≥ 7 days of treatment. If a participant receives rescue treatment with systemic corticosteroids or non-steroidal systemic immunosuppressive drugs (cyclosporine, methotrexate, mycophenolate mofetil, azathioprine, etc.) study treatment will be immediately discontinued. After the treatment with these medications is completed, study treatment may be resumed if deemed appropriate by the Investigator and the Study Physician, but not sooner than 5 half-lives after the last dose of systemic rescue medication. All participants will complete the schedule of study visits and assessments whether or not they complete study treatment and whether or not they receive rescue treatment for AD.

Participants who require any rescue therapy during the study will be classified as nonresponders from the time of rescue use up until week 16 in the primary analysis (see section 9.4.1). Sensitivity analyses will explore the impact of potential rescue use on the statistical analyses.

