8.1.6 Patient-reported Outcomes

Participants will complete all patient-reported outcomes (PRO) assessments using a handheld device. The handheld device will be the only accepted source of PRO data.

The Investigator will ensure that participants are properly trained on the use of this device and the importance of completing assessments as scheduled.

The handheld PRO device will be programmed at Visit 1 with reminder alarms for the daily diary. Study site staff will be able to adjust alarms for specific participant needs as needed. The participant will be required to complete a training module (at the site) before taking the device home.

The Investigator or designee will be responsible for ensuring that the participant is completing the daily diary and follow-up as necessary to minimize missing data. Participant compliance should be checked weekly (at a minimum) to ensure that the participant is completing the assessments as scheduled. Monitoring of participant compliance with completion of the diary is especially critical between Visit 1 and Visit 2 to ensure that the participant meets applicable criteria for randomization. If the participant does not meet the randomization requirements, the device will be deactivated and retained at the site for future use.

Review of participant compliance with the assessment schedule, completion of any available assessments, and logging of the visit on the handheld device should be completed prior to other study procedures.

Compliance with the assessment schedule should be completed weekly throughout the study and follow-up with participants via phone and at the visits. Compliance review is required to ensure sufficient data are available for supporting the primary endpoint of this study.

The timing and frequency for each PRO is provided in Table 3.

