The sample size calculations that follow are based on the primary endpoint, ie, the proportion of patients with an IGA 0/1 and a decrease in IGA of ≥ 2 points relative to baseline. The calculations are associated with differences between benralizumab 30 mg Q4W and placebo at Week 16 during the initial double-blind, placebo-controlled phase of the study (Figure 2). For the primary analysis, the sample size calculation will power the study to detect a difference between benralizumab 30 mg Q4W and placebo in the overall population. Additional calculations have been provided to ensure that the study is adequately powered to detect treatment differences and consistency of effect in potential subgroups, should efficacy be limited to a subset of the population.

Primary analysis: In the overall population, a minimum of 80 participants per treatment group will provide a high level of power (> 95%) to detect a 30% difference between benralizumab 30 mg Q4W and placebo for the primary endpoint. This calculation is based on a 2-sided test and a 5% significance level and assumes a response rate of 40% for benralizumab 30 mg Q4W and 10% for placebo.

Subgroup analyses: As a benchmark, a minimum of 35 participants per treatment will provide at least 80% power to detect a 30% difference between benralizumab 30 mg Q4W and placebo. (As for the primary analysis, these calculations are based on a 2-sided test and a 5%

significance level, and assumes the same response rates for benralizumab 30 mg Q4W and placebo.) Thus, there is a high probability of detecting differences between treatments in the baseline blood eosinophils \geq 300 cells/µL subgroup (with 50 participants per treatment), in the adult subgroup (with 40 participants per treatment), and in the adolescent subgroup (with 40 participants per treatment). Note that in the baseline blood eosinophils < 300 cells/µL subgroup, 30 participants per treatment group will provide an adequate amount of data to explore treatment differences, and will allow different cut-offs between 'low' and 'high' eosinophils at baseline to be assessed.

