9.4.1 General Considerations

The primary analysis will be based on the initial 16-week, double-blind, placebo-controlled phase of the study, and will compare 2 treatment groups comprising all participants

randomized to benralizumab 30 mg Q4W until Week 16 (n = 80) and all participants randomized to placebo until Week 16 (n = 80).

The primary estimand will be based on participants in the full analysis set (Table 12) and will be used for the analysis of primary and key secondary endpoints. The set of incurrent events for this estimand consists of participants who withdraw from the study and participants who require rescue therapy (refer to Section 6.5.3). The primary estimand will regard these participants as non-responders from the time such events occur up to Week 16. The amount of missing data for this study is expected to be low, as participants who prematurely discontinue IP will be asked to come in for all visits and complete all study assessments up to the end of the study. Any participant with missing data at a specific time point will be considered as a non-responder at that time point.

Additional estimands will be specified in the SAP for the primary and key secondary endpoints to carry out sensitivity analyses for assessing the robustness of results. These sensitivity analyses will explore different methods for handling intercurrent events and different assumptions for missing data. Estimands for secondary, exploratory, and tertiary endpoints will also be specified in the SAP, which will include how intercurrent events will be handled for continuous endpoints. Sensitivity analyses may be carried out for specific secondary endpoints, if deemed necessary to strengthen conclusions drawn from the primary and key secondary endpoints. Full details will be provided in the SAP.

Full details of the analyses and methods to be used for the extension period will be provided in the SAP.

Demography and baseline characteristics will be summarized by treatment for the Full Analysis Set (FAS). If there are major differences between the FAS and safety analysis set, the summaries will also be repeated and presented for the safety analysis set.

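### After early IP discontinuation, Section 7.1.1.1 names no reduced schedule that keeps the Week 16 endpoint visit, so some participants last dosed at Week 0, 4 or 8 lose data the estimand asks for

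*Protocol*

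**What the plan says.** Section 7.1.1.1 sets out two routes at the IP discontinuation (IPD) visit. The first is attendance at all scheduled visits with all procedures but without IP. The second is for a participant unwilling or unable to attend: "he/she will be offered a follow-up option that includes monthly telephone contact instead". The calls cover concomitant medication, AD symptoms and adverse events.

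Other provisions bear on what this route loses:

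- IGA and EASI are completed by the investigator on a site device (Sections 8.1.1 and 8.1.2).
- For patient-reported outcomes, "The handheld device will be the only accepted source of PRO data" (Section 8.1.6). Table 4 schedules POEM and DLQI/CDLQI "At site at V1, V2, V3, V4, V5, V6, V9, V12, V15, and V16", while the Peak Pruritus NRS is recorded every evening at home.
- The IPD visit falls 4 weeks ± 7 days after the last dose, includes IGA, EASI and SCORAD, and replaces the nearest regular visit (Table 3 and its footnote d).
- The intercurrent events are study withdrawal and rescue therapy only. A missing value is scored as non-response (Sections 9.1 and 9.4.1).
- Section 6.5.3 states: "All participants will complete the schedule of study visits and assessments whether or not they complete study treatment". Section 9.4.1 states: "The amount of missing data for this study is expected to be low", on the ground that participants who stop IP will be asked to attend all visits.

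**The concern.** Because stopping IP is not an intercurrent event, the primary estimand asks for the actual Week 16 status of an unrescued participant who stops IP and stays in the study. The telephone route cannot supply that status for IGA or EASI, so an assumed non-response replaces a value that one visit could have recorded. The continuous endpoints (EASI, SCORAD, POEM, DLQI/CDLQI) have no non-responder rule and simply lack a Week 16 value. The sensitivity analyses planned in Section 9.4.7 then have fewer observed off-treatment outcomes to inform them.

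Two things are at stake: dilution of the estimated difference, and bias if the share lost differs between arms. The text also disagrees with itself, because Section 6.5.3 has everyone completing the visit schedule while Section 7.1.1.1 offers a way out of it.

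**Working it through.** **The plan's own figure.** Section 9.2 says "a minimum of 80 participants per treatment group will provide a high level of power (> 95%) to detect a 30% difference" and "assumes a response rate of 40% for benralizumab 30 mg Q4W and 10% for placebo"; "This calculation is based on a 2-sided test and a 5% significance level". With a pooled-variance normal approximation,

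z = (Δ√n − 1.96·√(2p̄(1−p̄))) / √(p₁(1−p₁) + p₂(1−p₂)).

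For n = 80, p₁ = 0.40, p₂ = 0.10 and p̄ = 0.25: z = (0.30 × 8.944 − 1.96 × 0.6124) / 0.5745 = 2.58, so power is 99.5%. The stated figure is reproduced.

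**Who is exposed before Week 16.** Doses are given at Weeks 0, 4, 8 and 12 (Section 4.1.2). The IPD visit comes about 4 weeks after the last dose:

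| Last dose | IPD visit at about | Week 16 IGA/EASI/SCORAD on the telephone route |
|---|---|---|
| Week 0 | Week 4 | not collected |
| Week 4 | Week 8 | not collected |
| Week 8 | Week 12 | not collected |
| Week 12 | Week 16 | collected at the IPD visit |

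**Numbers affected.** The protocol gives no rates, so these are assumptions: 5% to 20% stop before Week 16, stops are spread evenly over the four doses (so 3/4 are exposed), and half of those exposed choose telephone contact.

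- Share lost per arm: 0.05 × 0.75 × 0.5 = 1.875%, up to 0.20 × 0.75 × 0.5 = 7.5%.
- Count per arm: 80 × 1.875% = 1.5, up to 80 × 7.5% = 6.

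**Dilution with equal loss.** Points lost = share lost × (benralizumab minus placebo response among those lost).

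| Response among those lost | Low (1.875%) | High (7.5%) |
|---|---|---|
| 10% vs 2% | 8 × 0.01875 = 0.15 | 8 × 0.075 = 0.6 |
| 25% vs 5% | 20 × 0.01875 = 0.375 | 20 × 0.075 = 1.5 |
| 40% vs 10% | 30 × 0.01875 = 0.56 | 30 × 0.075 = 2.25 |

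These figures do not subtract participants who are non-responders anyway because of rescue.

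**Power with equal loss.** Both planning rates are multiplied by (1 − loss), which assumes that those lost respond at their arm's full rate.

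| Loss | Difference | n = 80 per arm | n = 40 per arm (adults or adolescents) |
|---|---|---|---|
| 0% | 30.0 points | 99.5% | 88.7% |
| 5% | 28.5 | 99.2% | 86.4% |
| 10% | 27.0 | 98.8% | 83.8% |
| 20% | 24.0 | 97.3% | 77.6% |

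The assumed loss of 1.875% to 7.5% lies within the first three rows.

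**Unequal loss with no true difference.** The spurious difference is the common rate × (placebo loss − benralizumab loss). At the two ends of the assumed range (7.5% vs 1.875%) it is 0.10 × 5.625 = 0.56 points at a 10% rate and 0.40 × 5.625 = 2.25 points at a 40% rate. Larger gaps give more: 10% × (15% − 5%) = 1 point, and 40% × (20% − 5%) = 6 points. Those two cases use losses above the assumed range.

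**The case against.** The strongest reply is that the route is a retention fallback, offered only after full attendance has been encouraged and only to someone unwilling or unable to attend. It includes telephone contact, so it does not forbid a Week 16 visit, and Section 7.3 requires sites to reschedule missed visits. People reluctant to attend may also decline one visit. Section 9.4.1 says only that stoppers will be asked to come, which agrees with the first route. All of this stands. It lowers the expected yield, but it does not supply the missing option, and a site will work from the options that are named.

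A reader might infer more than the documents support:

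- That every stopper's Week 16 result is lost. It is not: with a last dose at Week 12, the IPD visit is itself at about Week 16.
- That all key secondary endpoints are lost. The pruritus diary is kept daily at home, device return is stated only for study withdrawal (Section 7.2), and Section 8.1.6 continues weekly compliance review throughout the study. The protocol is silent on the diary during telephone follow-up; it does not end it.
- That each recovered visit would change a primary result. Section 7.1.1 provides standard of care after permanent discontinuation. Where that care counts as rescue, the participant is a non-responder up to Week 16 regardless.
- That loss is known to differ by arm. This is plausible, but the documents give no figure for it.

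For the continuous endpoints, visits up to and including the IPD visit still contribute to the repeated-measures model.

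**Conclusion.** The point holds as a cheap improvement. For participants last dosed at Week 0, 4 or 8 who choose telephone contact, the protocol gives up Week 16 IGA, EASI and SCORAD data that its own estimand asks for. Section 6.5.3 does not fit Section 7.1.1.1; Section 9.4.1 is only an expectation, but it does not allow for the telephone route.

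The size is small. Under the stated assumptions, 1.5 to 6 of 80 per arm are affected, and the dilution is about 0.4 to 1.5 points at 25% vs 5% response, with a range of 0.15 to 2.25 and less after overlap with rescue. Every rate behind these figures is assumed. A reader might conclude that the trial's power is at risk, but overall power stays above 97% even at 20% equal loss. Only in subgroups of 40 per arm does it fall below 80%, and only near 20% loss. What remains is avoidable missing data, and possible bias if the loss differs by arm.

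**What to change.** In Section 7.1.1.1:

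- Add an intermediate option, offered before telephone-only contact: telephone contact plus one on-site Week 16 visit (Week 52 if IP stops in the extension) with IGA, EASI, SCORAD and the site patient-reported outcomes. Telephone-only contact remains for those who decline.
- State that participants in telephone follow-up keep the handheld device and continue the daily Peak Pruritus NRS.

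Reword Sections 6.5.3 and 9.4.1 so that they agree with these routes. Home completion of POEM and DLQI/CDLQI on the device could be allowed; the device already takes EQ-5D-5L and SF-36v2 at home. This is optional, because it would mix home and site completion for a few participants.

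The cost is a few sentences in an amendment. Both visits are already in the schedule. Uptake is uncertain among participants reluctant to attend, so recovery will probably be partial.

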AEs, Vital signs, and Clinical laboratory values. Assessments related to AEs cover: • Occurrence/frequency
 Relationship to IP as assessed by Investigator Intensity Seriousness Death AEs leading to discontinuation of IP Vital signs parameters include systolic and diastolic blood pressure, and pulse, as well as respiration rate, body temperature, body weight, and height. Assessments related to vital signs cover: Observed value Absolute and percent change from baseline values over time
Rate of AD-related healthcare resource utilization during the study
Change from baseline in scores for: • HADS • PGI-S • SF-36v2 Health Survey • EQ-5D-5L • CCI • Patient-reported experience (free text entry)

Table 5 Objectives and Endpoints

1 1010 0	objecures and Enopoints		
CCI			
To explore the us clinical efficacy a	se of skin photography to inform assessments	 Concordance with in-person assessments of clinical efficacy. 	
a The locally-approved regimen of topical medication.			
 The key secondary endpoints will use the same estimand as outlined for the primary endpoint. For all other endpoints, the estimands will be detailed in the SAP. 			
CCI ; AD, Atopic dermatitis; ADA, anti-drug antibodies; AE, adverse event;			
CDLQI, The Children's Dermatology Life Quality Index; DLQI, Dermatology Life Quality Index; EASI,			
Eczema Area and Severity Index; EQ-5D-5L, European Quality of Life-5 Dimensions; HADS, Hospital Anxiety			
and Depression Scale; IGA, Investigator Global Assessment; IP, investigational product; CCI			
; PGI-S, Patient Global Impression of Severity; PK, pharmacokinetics; POEM, Patient			

CCI (CCI); PGI-S, Patient Global Impression of Severity; PK, pharmacokinetics; POEM, Patient Oriented Eczema Measure; Q4W, every 4 weeks; Q8W, every 8 weeks; CCI ; SAP, Statistical Analysis Plan; SCORAD, SCORing Atopic Dermatitis; SF-36v2, Short Form 36-item Health Survey Version 2; CCI

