8.8 Healthcare Resource Utilization

AD-related healthcare resource utilization information will be collected by the Investigator, or designee, in accordance with the SoA (Table 3) and recorded in the appropriate eCRF module. Protocol-mandated procedures, tests, and encounters are not included.

At randomization, retrospective AD-related healthcare resource utilization information will be collected with a one-year recall period. At all subsequent visits, AD-related healthcare resource utilization information will be collected with a recall period of 'since last scheduled visit'.

The data collected may be used to conduct exploratory economic analyses and include:

- Number and duration of hospitalization (length of stay, overall and by wards [eg, general ward, intensive care unit])
- Number and type of diagnostic and therapeutic tests and procedures
- Number of outpatient medical encounters and interventions (including GP, specialists, or emergency room visits, and medications)

Note: Cases of hospitalization occurring after signing of the ICF must be reported as an SAE (Section 8.3).

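### Telephone-only follow-up after stopping treatment does not collect AD-related healthcare resource use, which leaves treatment-linked gaps in an exploratory rate endpoint

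*Protocol*

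**What the plan says.** Section 7.1.1.1 sets two follow-up routes after early discontinuation of IP.

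- **Default route:** "Participants are encouraged to return to all scheduled site visits and perform all procedures", without IP, to the end of the study at Visit 16.
- **Fallback route:** "If the participant is unwilling or unable to attend the scheduled site visits", the participant is offered an option that includes monthly telephone contact. At these contacts "the Investigator will collect information about concomitant medications, information on AD symptoms, and AE/SAE(s").

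Table 3 marks healthcare resource utilization at Visits 2 to 16 and at the IP discontinuation visit. It is not marked at unscheduled visits, and the table has no telephone entry. Section 8.8 ties collection to visits: after the one-year look-back at randomization, "AD-related healthcare resource utilization information will be collected with a recall period of 'since last scheduled visit". The data cover hospital stays, diagnostic and therapeutic tests and procedures, and a third item: "Number of outpatient medical encounters and interventions (including GP, specialists, or emergency room visits, and medications"). Section 8.8 also notes: "Cases of hospitalization occurring after signing of the ICF must be reported as an SAE".

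Table 5 lists the endpoint as "Rate of AD-related healthcare resource utilization during the study". Section 8.8 says that the data may serve exploratory economic analyses. Section 9.4.2.4 leaves the analysis of exploratory objectives to the SAP or an exploratory analysis plan.

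**The concern.** Section 7.1 states that stopping IP is not withdrawal from the study. A participant on telephone follow-up is therefore still in the study, and that time falls within the period that the endpoint names. For part of what the endpoint counts, however, nothing is asked during that time.

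The gap is not random with respect to treatment, because it arises only after a participant stops IP. Section 7.1.1 says that those who stop permanently are given locally available standard of care, so their pattern of service use may change at the point where collection ceases. What is at stake is the completeness of one exploratory endpoint. The gap lies in data collection, and an analysis plan cannot recover data that were never collected.

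**Working it through.** The protocol gives no resource-use rate, no expected share on telephone follow-up and no person-time rule, so there is no stated figure to reproduce. The check is a comparison of sections, followed by algebra that shows what the size and direction depend on.

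**Step 1. Components in section 8.8 against the telephone items in section 7.1.1.1**

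| Component | Route by telephone? |
|---|---|
| Hospitalization | Yes, as an SAE |
| Medications | Yes, as concomitant medications; section 6.5 also records the reason for use |
| GP, specialist and emergency encounters | None listed |
| Diagnostic and therapeutic tests and procedures | None listed |

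The AE item does not close the gap. Section 8.3.6 says that events unequivocally due to AD are not reported as AEs unless they meet SAE criteria or lead to discontinuation of IP. An AD flare seen by a specialist or in an emergency room without admission would usually not appear there. The AD-symptoms item asks about symptoms, not about services used.

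**Step 2. How long the gap can last**

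Section 7.1.1.1 frames the telephone option by reference to attendance until the end of the double-blind treatment period. Sections 4.1 and 4.1.2 use that term for the first 16 weeks. Table 3 also labels the extension as double-blind, up to Week 52. The default route runs to Visit 16, at Week 60.

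As an assumed example, take a last dose at Week 8. The IP discontinuation visit falls 4 weeks later, at Week 12. Time after that visit is then:

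- to Week 16: 16 − 12 = 4 weeks
- to Week 52: 52 − 12 = 40 weeks
- to Week 60: 60 − 12 = 48 weeks

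The wording does not settle which applies.

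**Step 3. What the gap does to the rate**

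Consider one participant and only the components with no telephone route. Let the last resource-use assessment be at week w and the end of follow-up at week T. Let the event rate be r up to w and k·r afterwards.

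- True rate over follow-up: r[w + k(T − w)] / T
- Recorded events: r·w
- Recorded ÷ true, denominator T: w / [w + k(T − w)]
- Recorded ÷ true, denominator w: T / [w + k(T − w)]

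The first ratio is below 1 for any k above 0. The second is exactly 1 when k = 1, below 1 when k exceeds 1, and above 1 when k is less than 1. At arm level the effect shrinks with the share of participants on telephone-only follow-up.

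The protocol gives none of w, T, k, that share or the denominator. It follows that the gap can bias the rate, that its size and direction are open, and that a careful denominator removes the problem only if service use is unchanged after stopping.

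**The case against.** The strongest objection is that the rate's denominator is not in the protocol. It belongs to the SAP or exploratory plan, which is not at hand and may limit person-time to periods with an assessment. That stands. A reader might infer that unobserved time necessarily dilutes the rate in everyone who stops treatment, and might attach a large percentage to this. The protocol does not support that inference:

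- It does not say that unobserved time is counted.
- It makes full site attendance the default after stopping, so only those who also will not or cannot attend are affected.
- It still captures hospitalizations and medications by telephone.
- It does not clearly run telephone contact to Week 60.

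A reader might also infer that a regimen with more stopping would look cheaper. Nothing in the protocol shows that resource use rises after stopping or that stopping differs between sequences.

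Other points also have weight. Section 9.4.1 expects little missing data. Because recall runs from the last scheduled visit, a participant who returns to site visits could report part of the gap. The telephone option is said to include these contacts, so it is not stated to be limited to them. The endpoint is exploratory and outside the testing hierarchy of section 9.4.6.

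What remains is narrower. The protocol names the items asked at each call, and resource use is not among them.

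**Conclusion.** The point holds as a minor gap in data collection. For participants who stop IP and are then followed only by telephone, outpatient and emergency encounters, tests and procedures have no planned route into the data. An exploratory endpoint defined over the study therefore has gaps linked to stopping treatment.

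This can bias the rate, but no size or direction can be stated from the protocol. The size depends on the number of participants using the telephone option, its duration and the denominator chosen later; the direction also depends on how service use changes after stopping. The conclusion assumes that sites ask only the listed items. It has no bearing on the primary, key secondary or safety results.

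**What to change.** In section 7.1.1.1, add AD-related healthcare resource utilization since the last contact to the items collected at each monthly telephone contact. Make the matching change in section 8.8 and Table 3, and enable the existing eCRF module for telephone contacts. The calls are already planned, so the cost is a few extra questions and a small eCRF change. The downsides are slightly longer calls and dependence on recall by telephone.
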